### **9.7.2       Interim Analysis**

After the last study participant has completed the Week 48 visit, or after the last study participant has prematurely discontinued prior to reaching Week 48, an unblinded interim analysis will be performed and a corresponding interim clinical study report (CSR) may be written. The purpose of this interim analysis is to perform a comprehensive evaluation of all available double-blind data to prepare regulatory submissions for approval of the HS indication. A final analysis and updated final CSR will be prepared once all data (through to the SFU visit) have been collected.

## **9.8       Determination of sample size**

A total of 490 study participants will be randomly assigned in a 2:2:2:1 ratio to the following treatment arms:

- Bimekizumab 320mg Q2W during Initial Treatment Period (Weeks 0-16) and Maintenance Treatment (Weeks 16-48) Periods, N=140
- Bimekizumab 320mg Q2W during Initial Treatment Period (Weeks 0-16), and Bimekizumab 320mg Q4W during Maintenance Treatment Period (Weeks 16-48), N=140
- Bimekizumab 320mg Q4W during Initial Treatment (Weeks 0-16) and Maintenance Treatment Periods (Weeks 16-48), N=140
- Placebo during Initial Treatment Period (Weeks 0-16), and Bimekizumab 320mg Q2W during Maintenance Treatment Period (Weeks 16-48), N=70

The analysis of the primary efficacy endpoint and secondary efficacy endpoints are based on a comparison of bimekizumab versus placebo at Week 16, with alpha adjustment strategy as indicated in Section 9.3.1 and Section 9.3.2.

The power to detect a statistically significant difference for each of the endpoints are shown in Table 9-1. Notably, with a 2-sided significance level of 0.025, the sample size of 140:70

provides 73% power for detecting at least a difference of 1.5 (bimekizumab Q4W vs placebo) for the Worst Pain change from Baseline (CFB) endpoint.

Given the high level of power for each of the primary and key secondary endpoints at the 0.025 significance level for the Q2W comparison (power $\geq$ 0.89), and per the alpha spending strategy, there is a high likelihood that the Q4W comparison of Worst Pain CFB vs placebo will be allowed to be tested against the 0.05 level of significance. The power for this latter test is 81%. The sample size is thus ultimately driven by the Worst CFB endpoint. Furthermore, the randomization ratio of 2:2:2:1 has been chosen to provide study participants with a high probability (6/7 ~ 86%) of being randomized to active study drug.

After randomization for this study was complete, an additional endpoint to assess Worst Pain response was included in the sequential testing procedure. This additional endpoint is defined as HSSDD weekly worst skin pain score at or beyond the threshold for clinically meaningful change at Week 16. Note that the power calculations reported in [Table 9-1](#) for this endpoint are based on the sample size that was initially driven by the Worst Pain CFB endpoint as described above. With a 2-sided significance level of 0.025, the sample size of 104:52 in the subset of participants reporting Baseline HSSDD worst skin pain score at or beyond the threshold for clinically meaningful change (ie, Baseline HSSDD  $\geq$ threshold value) provides 53% power for detecting a statistically significant difference between bimekizumab Q4W and placebo in the proportion of Worst Pain responders.

Note that the power at the 0.025 level of significance associated with this endpoint for the comparison between bimekizumab Q2W and placebo is 95%. The Q4W comparison of Worst Pain response vs placebo against the 0.05 level of significance is therefore likely, and the power at this significance level is 65%. Given the strength of the power for the bimekizumab Q2W arm vs placebo across endpoints, it is considered acceptable to have a relatively low power for this final endpoint in the testing sequence for the bimekizumab Q4W treatment arm vs placebo.

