## **9.3 Planned efficacy/outcome analyses**

### **9.3.1 Analysis of the primary efficacy endpoint**

The primary objective of this randomized, double-blind, placebo-controlled, multicenter, pivotal study in study participants with moderate to severe HS is to compare the efficacy of bimekizumab 320mg Q2W and bimekizumab 320mg Q4W with placebo at Week 16. For the purposes of Week 16 analyses, the bimekizumab treatment arms of 320mg Q2W/Q2W and bimekizumab 320mg Q2W/Q4W treatment groups will be pooled.

The primary and secondary efficacy analyses will be performed based on the RS.

The primary endpoint is the HiSCR50 response at Week 16. The primary efficacy analysis will evaluate the composite estimand in the RS. The composite estimand combines the clinically meaningful improvement from Baseline based on the HiSCR50 response and early receipt of

systemic antibiotic rescue medication, or discontinuation of IMP due to an AE or lack of efficacy.

The following 4 attributes describe the estimand that will be used to define the treatment effect of interest for the primary efficacy analysis:

4. Population=Study participants meeting the protocol-specified inclusion/exclusion criteria.
5. Study participant-level outcome=HiSCR50 at Week 16.
6. Intercurrent event handling=An intercurrent event is defined as receipt of systemic antibiotic rescue medication or discontinuation of study treatment due to an AE or lack of efficacy prior to Week 16. A composite strategy will be implemented in which a positive clinical outcome is defined as achieving HiSCR50 at Week 16 and not receiving systemic antibiotic rescue medication, and not discontinuing study treatment due to an AE or lack of efficacy through Week 16. Any missing data at Week 16 that are not preceded by an intercurrent event will be imputed using multiple imputation.
7. Population-level summary measure=conditional odds ratio comparing bimekizumab to placebo adjusted for stratification factors used in the randomization.

As a sensitivity analysis, any missing data at Week 16 that are not preceded by an intercurrent event (ie, receipt of systemic antibiotic rescue medication, or discontinuation of IMP due to an AE or lack of efficacy) will be imputed as non-response.

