### **9.3.2 Analysis of the secondary efficacy endpoints**

The secondary efficacy variables supporting the primary efficacy variable are listed below, and will be included in the multiplicity adjustment:

1. Proportion of study participants who achieve HiSCR75 at Week 16. A similar analysis to the primary responder analysis will be performed.
  - a. bimekizumab 320mg Q2W vs placebo
  - b. bimekizumab 320mg Q4W vs placebo
2. Absolute change from Baseline in DLQI Total Score at Week 16. Analysis will be based on an analysis of covariance (ANCOVA) with treatment and stratification variables as fixed effects and the Baseline values as covariate.
  - a. bimekizumab 320mg Q2W vs placebo

---

- b. bimekizumab 320mg Q4W vs placebo
- 3. Absolute change from Baseline in Skin Pain Score at Week 16, as assessed by the “worst pain” item (11-point numeric rating scale) in the HSSDD. Analysis will be based on an ANCOVA with treatment and stratification variables as fixed effects and the Baseline values as covariate.
  - a. bimekizumab 320mg Q2W vs placebo
  - b. bimekizumab 320mg Q4W vs placebo
- 4. Pain response (defined as a decrease from Baseline in HSSDD weekly worst skin pain score at or beyond the threshold for clinically meaningful change) at Week 16. A similar analysis to the primary responder analysis will be performed.
  - a. bimekizumab 320mg Q2W vs placebo
  - b. bimekizumab 320mg Q4W vs placebo

[figure not shown]
To control the overall type I error rate at 0.05 for the multiple comparisons in the primary and secondary efficacy variables, a closed testing procedure under a parallel gatekeeping framework will be applied ([Sun, 2018](#)).

Under this framework, each bimekizumab dose of 320mg Q2W and 320mg Q4W will be compared to placebo in the first instance at a familywise error rate of 0.025 ( $\alpha/2$ ). Simultaneously within each dose, closed testing for the primary and secondary efficacy endpoints will be performed as follows:

- 1. Step 1: Test  $\text{HiSCR}_{50}$  at significance level 0.025.
- 2. Steps 2 to 5 – If Step 1 is significant at 0.025 then test each secondary endpoint sequentially in the order shown below, moving to the next step only if significance achieved at 0.025.
- 3. In the event that Step 5 is significant at 0.025 for a given dose, then Steps 1 to 5 will be repeated for the other dose using a significance level of 0.05.

A schematic of the procedure is shown in [Figure 9–1](#).

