**Table 9–1: Power calculation assumptions and methods**

Endpoint	Power $\alpha = 0.025$ , 2-sided		Assumptions		
	Q2W	Q4W	Week 16 Bimekizumab Q2W N=280 a	Week 16 Bimekizumab Q4W N=140	Week 16 Placebo N=70
HiSCR 50	0.99	0.90	Proportion responders=0.60	Proportion responders=0.50	Proportion responders=0.25
HiSCR 75	0.99	0.98	Proportion responders=0.45	Proportion responders=0.35	Proportion responders=0.10
DLQI	0.99	0.96	Mean CFB=-5.4; SD=6.8	Mean CFB=-4.8; SD=6.8	Mean CFB=-0.8; SD=6.6
Worst Pain CFB b	0.89	0.73	Mean CFB=-2.2; SD=3.2	Mean CFB=-2.0; SD=3.2	Mean CFB=-0.5; SD=3.7
Worst Pain Response c	0.95	0.53	Proportion responders=0.53	Proportion responders=0.43	Proportion responders=0.23

CFB=change from Baseline; Q2W=every 2 weeks; Q4W=every 4 weeks; SD=standard deviation

Note: Estimates for HS0003 are based on Week 12 data from the HS0001 study.

a Pooled Q2W at Week 16 from Q2W/Q2W and Q2W/Q4W arms

b Within-subject average of Worst Pain according to 24-hour recall

c Assumes N=208, 104, 52 in Q2W, Q4W, and placebo, respectively, to account for Worst Pain score at or above the threshold for clinically meaningful change from Baseline

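### The ranked pain-response endpoint is powered in participants with Baseline pain at or above the threshold but defined and analysed in all randomized participants, so the stated power is not that of the planned test

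*Protocol*

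**What the plan says.** All places are in the protocol.

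- **Endpoint.** Section 9.3.2 lists pain response as the fourth secondary endpoint, a "decrease from Baseline in HSSDD weekly worst skin pain score at or beyond the threshold for clinically meaningful change) at Week 16", analysed like the primary responder endpoint. Sections 1.1 and 3 use the same definition. None of the three sets a condition on the Baseline score.
- **Analysis set.** Section 9.3.1 states: "The primary and secondary efficacy analyses will be performed based on the RS". Section 9.1.2 defines that set as everyone randomized, which Section 9.8 puts at 280 (pooled Q2W), 140 (Q4W) and 70 (placebo).
- **Power.** Section 9.8 quotes 53% power for Q4W at two-sided 0.025 with "the sample size of 104:52 in the subset of participants reporting Baseline HSSDD worst skin pain score at or beyond the threshold". It also gives 65% for Q4W at 0.05 and 95% for Q2W at 0.025. Footnote c of Table 9-1 reads: "Assumes N=208, 104, 52 in Q2W, Q4W, and placebo, respectively, to account for Worst Pain score at or above the threshold". The assumed response rates are 0.53 (Q2W), 0.43 (Q4W) and 0.23 (placebo).
- **Place in the testing order.** Pain response is Step 5, the last step within each dose. Success there at 0.025 allows the other dose to be tested at 0.05.

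**The concern.** One confirmatory test has two populations. The power section uses only participants whose Baseline pain leaves room for a response; the endpoint and analysis sections use everyone randomized. In the full set, participants below the threshold at Baseline count in the denominator but can never count as responders. That pulls the response rates and the odds ratio down in every arm.

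The protocol states this kind of restriction where it wants one. In Section 3, the unranked 30%-reduction pain endpoints are limited to a Baseline score of at least 3, and the DLQI responder endpoint to a Baseline score of at least 4. The ranked pain endpoint, which matters more, carries no such limit.

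At stake is the definition of Step 5. For Q2W, success at Step 5 releases level 0.05 for every Q4W test. A team working from Section 9.3.1 and a team working from Section 9.8 would report different denominators, response rates and odds ratios, and in some trials a different decision at that gate. The endpoint was also added after randomization was complete, so its population should be beyond doubt before the data are unblinded.

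**Working it through.** **Inputs** (Section 9.8 and Table 9-1)

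| | Q2W | Q4W | Placebo |
|---|---|---|---|
| Randomized | 280 | 140 | 70 |
| At or above threshold (planned) | 208 | 104 | 52 |
| Assumed response rate | 0.53 | 0.43 | 0.23 |

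**Step 1. Share who cannot respond.** 208 + 104 + 52 = 364, and 490 − 364 = 126, which is 126/490 = 25.7%. The share is the same in each arm (36/140 = 18/70 = 72/280). I take the 11-point scale to run from 0, so a decrease cannot exceed the Baseline score.

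**Step 2. Reproduce the stated power on the subset.** The protocol does not name its power method. For a two-proportion chi-square test with continuity correction, the normal approximation is

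power = Φ[(d − z·se0)/se1], where
- d = |p1 − p2| − ½(1/n1 + 1/n2)
- se0 = √[p̄(1 − p̄)(1/n1 + 1/n2)], with p̄ the pooled rate
- se1 = √[p1(1 − p1)/n1 + p2(1 − p2)/n2]

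Q4W at 0.025 (z = 2.241), 104:52:
- d = 0.20 − 0.0144 = 0.1856
- p̄ = 0.3633, se0 = 0.0817, se1 = 0.0759
- (0.1856 − 2.241 × 0.0817)/0.0759 = 0.03, so power = 0.513

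Exact enumeration of the same test gives 0.526. The continuity-corrected arcsine approximation (Walters) gives 0.540. The stated value is 0.53, so the subset is the population that was powered. With the same rates on 140:70, the exact corrected test gives 0.692, which does not match.

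**Step 3. Rates in the Randomized Set.** Participants below the threshold count as non-responders:
- Q2W: 0.53 × 208/280 = 0.394
- Q4W: 0.43 × 104/140 = 0.319
- Placebo: 0.23 × 52/70 = 0.171

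Odds ratios:
- Q2W: (0.53/0.47)/(0.23/0.77) = 3.78 falls to (0.394/0.606)/(0.171/0.829) = 3.15
- Q4W: 2.53 falls to 2.28

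**Step 4. Power in the Randomized Set.** Q4W at 0.025, 140:70:
- d = 0.1486 − 0.0107 = 0.1379
- p̄ = 0.2699, se0 = 0.0650, se1 = 0.0598
- (0.1379 − 2.241 × 0.0650)/0.0598 = −0.13, so power = 0.448

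Like-for-like results, subset → Randomized Set:

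| Test | Q2W, 0.025 | Q4W, 0.025 | Q4W, 0.05 |
|---|---|---|---|
| Stated (subset) | 0.95 | 0.53 | 0.65 |
| Corrected chi-square, exact | 0.952 → 0.907 | 0.526 → 0.454 | 0.641 → 0.579 |
| Arcsine (Walters) | 0.950 → 0.914 | 0.540 → 0.485 | 0.648 → 0.596 |
| Fisher, exact | 0.958 → 0.924 | 0.568 → 0.507 | 0.683 → 0.622 |
| Uncorrected chi-square, exact | 0.966 → 0.931 | 0.598 → 0.532 | 0.708 → 0.647 |
| Wald log odds ratio | 0.930 → 0.871 | 0.567 → 0.504 | 0.674 → 0.615 |

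Power falls under every test. The first two methods come closest to the stated figures.

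**Step 5. Dependence on the 74.3% share.** If the share at or above the threshold is instead 65% to 90%, Randomized Set power (Fisher) runs from 0.86 to 0.98 for Q2W, from 0.42 to 0.64 for Q4W at 0.025, and from 0.55 to 0.74 for Q4W at 0.05.

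**The case against.** Section 9.8 and the footnote to Table 9-1 name the subset openly, and the power is correct for the population they name. The protocol leaves the numerical threshold open and refers detail to a SAP that is not shown; a Baseline condition could be fixed there together with the threshold. No sentence says outright that participants below the threshold count as non-responders.

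The consequences are also limited. Baseline pain precedes treatment, so either population respects randomization and keeps type I error, provided one is chosen before unblinding. Responder counts are the same either way in complete data; only denominators differ. I simulated complete data with the Table 9-1 rates and an unadjusted Wald test: the two analyses reached the same significance decision in about 95% of trials for Q2W at 0.025, and for Q4W in about 87% at 0.025 and 88% at 0.05. The sample size was not set by this endpoint, and Section 9.8 already accepts low Q4W power for it.

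Most of this stands as a limit on the size of the problem. It does not remove the conflict. If the SAP restricts the population, it departs from Section 9.3.1; if it does not, Section 9.8 and Table 9-1 describe a different test. Disagreement in roughly 5% to 13% of trials is also not negligible for a gate in a confirmatory sequence.

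**Conclusion.** The point holds: the protocol contradicts itself on who is analysed at Step 5, and its stated power does not belong to the test it specifies. On a like-for-like method close to the stated figures, the loss is about 4 points for Q2W, 5 to 7 points for Q4W at 0.025 and 5 to 6 points for Q4W at 0.05.

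The size rests on the protocol's planning share of 104/140, which is not an observed figure, on its assumed response rates, and on a scale starting at 0. None of the formulas is the planned covariate-adjusted logistic regression with multiple imputation, so the differences are firmer than the levels. The contradiction itself depends on none of this: any nonzero share below the threshold makes the two analyses differ. The case for correction rests on the unsettled confirmatory population more than on the lost power.

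**What to change.** Choose one population and state it everywhere before unblinding.

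1. **Preferred, because it matches Section 9.8.** In Sections 1.1, 3 and 9.3.2, define the ranked endpoint as pain response among Randomized Set participants whose Baseline HSSDD weekly worst skin pain score is at or above the threshold. Name that subset as the analysis set for Step 5, as an explicit exception to Section 9.3.1.
2. **Alternative.** Keep the full Randomized Set, say that participants below the threshold count as non-responders, and restate Section 9.8 and Table 9-1 with 280, 140 and 70 participants, rates of 39%, 32% and 17%, and recalculated power.

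Either way, correct the sentence in Section 9.8 that introduces the endpoint: it describes a score at or beyond the threshold and omits that the measure is a decrease from Baseline.

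The cost is protocol and SAP wording. The first option reduces the number analysed at Step 5; the second means a slightly less favourable stated power. Neither needs more participants or new data.

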**Table 9–1: Power calculation assumptions and methods**

Endpoint	Power $\alpha = 0.025$ , 2-sided		Assumptions		
	Q2W	Q4W	Week 16 Bimekizumab Q2W N=280 a	Week 16 Bimekizumab Q4W N=140	Week 16 Placebo N=70
HiSCR 50	0.99	0.90	Proportion responders=0.60	Proportion responders=0.50	Proportion responders=0.25
HiSCR 75	0.99	0.98	Proportion responders=0.45	Proportion responders=0.35	Proportion responders=0.10
DLQI	0.99	0.96	Mean CFB=-5.4; SD=6.8	Mean CFB=-4.8; SD=6.8	Mean CFB=-0.8; SD=6.6
Worst Pain CFB b	0.89	0.73	Mean CFB=-2.2; SD=3.2	Mean CFB=-2.0; SD=3.2	Mean CFB=-0.5; SD=3.7
Worst Pain Response c	0.95	0.53	Proportion responders=0.53	Proportion responders=0.43	Proportion responders=0.23

CFB=change from Baseline; Q2W=every 2 weeks; Q4W=every 4 weeks; SD=standard deviation

Note: Estimates for HS0003 are based on Week 12 data from the HS0001 study.

a Pooled Q2W at Week 16 from Q2W/Q2W and Q2W/Q4W arms

b Within-subject average of Worst Pain according to 24-hour recall

c Assumes N=208, 104, 52 in Q2W, Q4W, and placebo, respectively, to account for Worst Pain score at or above the threshold for clinically meaningful change from Baseline

## **10 SUPPORTING DOCUMENTATION AND OPERATIONAL CONSIDERATIONS**

### **10.1 Appendix 1: Regulatory, ethical, and study oversight considerations**

#### **10.1.1 Regulatory and ethical considerations**

The study will be conducted under the auspices of an IRB/IEC, as defined in local regulations, International Council for Harmonisation (ICH)- Good Clinical Practice (GCP), and in accordance with the ethical principles that have their origin in the Declaration of Helsinki.

The Investigator/UCB will ensure that an appropriately constituted IRB/IEC that complies with the requirements of the current ICH-GCP version or applicable country-specific regulations will be responsible for the initial and continuing review and approval of the clinical study. Prior to initiation of the study, the Investigator/UCB will forward copies of the protocol, ICF, Investigator's Brochure, Investigator's curriculum vitae (if applicable), advertisement (if applicable), and all other participant-related documents to be used for the study to the IRB/IEC for its review and approval.

Before initiating a study, the Investigator will have written and dated full approval from the responsible IRB/IEC for the protocol.

The Investigator will also promptly report to the IRB/IEC all changes in the study, all unanticipated problems involving risks to participants or others, and any protocol deviations, to eliminate immediate hazards to participants.

The Investigator will not make any changes in the study or study conduct without IRB/IEC approval, except where necessary to eliminate apparent immediate hazards to the participants. For minor changes to a previously approved protocol during the period covered by the original approval, it may be possible for the Investigator to obtain an expedited review by the IRB/IEC as allowed.

As part of the IRB/IEC requirements for continuing review of approved studies, the Investigator will be responsible for submitting periodic progress reports to the IRB/IEC (based on IRB/IEC requirements), at intervals appropriate to the degree of participant risk involved, but no less than once per year. The Investigator should provide a final report to the IRB/IEC following study completion.

UCB (or its representative) will communicate safety information to the appropriate regulatory authorities and all active Investigators in accordance with applicable regulatory requirements. The appropriate IRB/IEC will also be informed by the Investigator or the Sponsor, as specified by the applicable regulatory requirements in each concerned country. Where applicable, Investigators are to provide the Sponsor (or its representative) with evidence of such IRB/IEC notification.

#### **10.1.2 Financial disclosure**

Insurance coverage will be handled according to local requirements.

Finance and insurance are addressed in the Investigator and/or CRO agreements, as applicable.

### **10.1.3 Informed consent process**

Study participant's informed consent must be obtained and documented in accordance with local regulations, ICH-GCP requirements, and the ethical principles that have their origin in the principles of the Declaration of Helsinki.

Prior to obtaining informed consent, information should be given in a language and at a level of complexity understandable to the study participant in both oral and written form by the Investigator (or designee). Each study participant will have the opportunity to discuss the study and its alternatives with the Investigator.

Prior to participation in the study, the ICF should be signed and personally dated by the participant, or his or her legal representative, and by the person who conducted the informed consent discussion (Investigator or designee). The study participant or his or her legal representative must receive a copy of the signed and dated ICF. As part of the consent process, each study participant must consent to direct access to his or her medical records for study-related monitoring, auditing, IRB/IEC review, and regulatory inspection.

If the ICF is amended during the study, the Investigator (or the Sponsor, if applicable) must follow all applicable regulatory requirements pertaining to the approval of the amended ICF by the IRB/IEC and use of the amended form.

All studies conducted at centers in the US must include the use of a Health Insurance Portability and Accountability Act Authorization form.

The study participant may withdraw his or her consent to participate in the study at any time. A study participant is considered as enrolled in the study when he or she has signed the ICF. A CRF must not be started, nor may any study specific procedure be performed for a given study participant, without having obtained his or her written consent to participate in the study.

